7.12 Study Intervention/Follow-up Compliance

Adherence to intervention will be monitored through therapist training and supervision:

Training will include: a) Review of treatment manual (1 hour) and videotaped training session describing the treatment protocol and therapeutic techniques (1 hour), followed by video or in-person Q&A session with a trainer (either the PI or a licensed clinical psychologist with expertise in “Engage”); b) role-play session with the trainer to practice skills; c) 3 practice sessions with an actor-patient to evaluate adherence to treatment using the “Engage Adherence Scales” adapted to Engage & Connect and “SRP Adherence Scale” adapted from previous psychotherapy trial which used a similar intervention (R01 MH096685, PI: [name]); d) Therapists will be required to achieve a ‘good’ fidelity score (≥ 4) on at least 3 sessions; e) Weekly supervision will focus on prevention of skill drift and maintenance of fidelity.

Therapy sessions will be video or audio-recorded for the purposes of supervision and evaluation of therapist adherence to the therapy protocol (e.g., therapist interventions, therapeutic interactions, etc.). These recordings will not be labeled with information such as participants’ name, date of birth, or other identifying information. Therapists will meet with a supervisor weekly for supervision, during

which corrective feedback will be provided to therapists that show “skill drift” (i.e. fidelity scores < 4). Recordings samples may be processed by a transcription service in order to obtain research grade transcriptions while maintaining privacy and data safety regulations. The files will only be labeled by an alphanumeric code and remain completely separate from any identifying information documentation. Because these recordings may include personal identifiable information (PII) or protected health information (PHI), we treat all samples as confidential data. Samples may be transcribed by study staff, TranscribeMe, or Speech to Text Watson IBM software. If needed, files will be transferred using Secure File Transfer protocols managed by WMC ITS. Speech to Text Watson IBM follows strict data safety regulations stores data on an encrypted cloud that requires user authentication for access, and all data are secured by encryption both while stored in the cloud and in transit.

Patient adherence to intervention (i.e. attendance) will be monitored by the PI and staff: We have developed procedures to minimize risk to our participants, increase retention, and create conditions that make study participation as comfortable as possible. To this end, we will educate participants regarding study procedure and commitment during the informed consent process. We will schedule appointments early in the day or at the participants’ convenience. Our team will call participants prior to each appointment to provide reminders and assist with transportation arrangements. Funds for transportation are included in our budget in order to increase accessibility. The PI or staff member will accompany participants to all MRI scans and be present during scanning sessions in order to maximize comfort and address any questions or concerns that may arise. The PI will collaborate with trained and experienced technicians at our MRI Center to reduce wait time and optimize efficiency of the MRI procedures. The PI will train study personnel in recruitment and data collection procedures with an emphasis on clear communication, sensitivity, and multicultural competence. These measures have led to high retention rates and participant satisfaction in our Institute’s randomized clinical trials. Based on data collected in previous psychotherapy trials at the Institute, we anticipate an attrition rate of ~10%, which has been incorporated into our power analyses.

8. Study Intervention Discontinuation and Participant Discontinuation/Withdrawal

8.1 Discontinuation of Study Intervention

Efforts will be made to increase retention and reduce dropout (see above). In the event that a participant chooses to discontinue the study, the PI and the clinician will discuss with the participant, identify reasons for discontinuation and invite the participant to continue to attend the remaining research assessments. The PI and staff will provide the participant with an appropriate referral for alternative treatment if needed and/or requested by the participant. In the event of an emerging suicide risk, the PI will follow procedure for suicide risk management (See Section 13 for full description of procedures). The study may be discontinued and the participant may be referred for outpatient or inpatient treatment based on clinical indication. If a patient is at imminent risk for harming themselves and unwilling to agree to psychiatric hospitalization, involuntary admission may be needed.

8.2 Participant Discontinuation/Withdrawal from the Study

- If any clinical adverse event (AE) or other medical condition or situation occurs such that continued participation in the study would not be in the best interest of the participant
- Worsening of depression symptoms and/or emerging suicide risk that warrants a higher level of care than provided within the study (e.g. psychiatric hospitalization).
- If the participant meets an exclusion criterion (either newly developed or not previously recognized) that precludes further study participation
- Participant lost to follow-up after several attempts to contact subject to schedule study visit.

The reason for participant discontinuation or withdrawal from the study will be recorded on the Case Report Form (CRF). Subjects who give informed consent and are randomized but do not receive the study intervention may be replaced. Subjects who give informed consent, and are randomized and receive the study intervention, and subsequently withdraw, or are withdrawn or discontinued from the study may be replaced.

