7.10 Duration of Follow Up

Participants who choose to discontinue the study will be asked and encouraged to complete research assessments for the remaining weeks per their agreement.

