12.6.2 Evaluation of Response

All subjects included in the study will be evaluated for treatment response at treatment end (See analysis plan above)

13. Adverse Event Reporting Requirements

Adverse event (AE) monitoring and reporting is a routine part of every clinical trial. The investigator will be required to provide appropriate information concerning any findings that suggest significant hazards, contraindications, side effects, or precautions pertinent to the safe use of the drug or device under investigation. Safety will be monitored by evaluation of adverse events reported by subjects or observed by investigators or research staff, as well as by other investigations such as clinical laboratory tests, x-rays, electrocardiographs, etc.

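### Participants withdrawn under section 8.2, including for worsening depression, are not covered by the request to continue research assessments, so some outcome data may be lost for outcome-related reasons

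*Combined protocol and SAP*

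**What the plan says.** Continued assessment appears twice, each time for voluntary stopping. Section 7.10: "Participants who choose to discontinue the study will be asked and encouraged to complete research assessments for the remaining weeks per their agreement". Section 8.1 opens the same offer with "In the event that a participant chooses to discontinue the study". Its heading concerns the intervention, but its text speaks of leaving the study, so the two are not kept apart.

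Section 8.2 covers withdrawal from the study for other reasons:

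- an adverse event or other circumstance that makes staying on against the person's interest;
- "Worsening of depression symptoms and/or emerging suicide risk that warrants a higher level of care than provided within the study", with psychiatric hospitalisation as the example;
- "If the participant meets an exclusion criterion (either newly developed or not previously recognized) that precludes further study participation";
- loss to follow-up.

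For these it requires that the reason be recorded on the CRF. It allows replacement, even after the intervention has begun. It says nothing about later MADRS, BADS or MRI assessments.

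Section 13.3 continues follow-up after discontinuation for adverse events only, and 8.3 is marked not applicable. Section 12.6.2 states that "All subjects included in the study will be evaluated for treatment response at treatment end", without saying how this applies to someone already withdrawn. Section 12 names no analysis set, missing-data method or sensitivity analysis.

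**The concern.** A participant withdrawn because depression has worsened leaves for a reason that is the MADRS outcome. If assessments then stop, the Week 9 scores that are missing tend to be the poor ones. The same holds for exclusions that develop during the study and follow from worsening, such as suicidal intent or psychotropic use (section 4.3).

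The visit schedule makes this concrete. Therapists give the PHQ-9 at every session (6.1.2), but MADRS is rated only at baseline and Weeks 3, 5 and 9 (6.1). Deterioration at sessions 6 to 8 can lead to withdrawal with no MADRS after Week 5. The PHQ-9 is not in the planned model (12.1, 12.4.1), so what prompted the withdrawal lies outside the analysis, and the mixed model cannot adjust for it.

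H1 to H3 are worded as change during Engage & Connect, and 12.4.1 names only time effects. A bias in within-arm change therefore enters the stated hypotheses directly. MADRS is a secondary endpoint, but BADS and the primary rsFC endpoint lose their remaining visits in the same way.

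**Working it through.** **Who is asked to continue.**

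| Reason for stopping | Later assessments requested? | Link to MADRS |
|---|---|---|
| Participant's choice | Yes (7.10, 8.1) | Varies |
| Worsening or suicide risk needing more care | Not stated (8.2) | Direct |
| Newly developed exclusion | Not stated (8.2) | Direct for some, e.g. suicidal intent or psychotropic use |
| Exclusion overlooked at entry | Not stated (8.2) | None stated; direction of bias unknown |
| Adverse event | AE follow-up only (13.3) | Varies |

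**Inputs from the plan.** Section 12.2 accrual: 11 + 14 + 17 + 18 = 60, made up of SRP 5 + 7 + 9 + 9 = 30 and Engage & Connect 6 + 7 + 8 + 9 = 30. Attrition is about 10% (4.1, 7.12): 0.10 × 60 = 6. The plan does not split these six by reason. They can include voluntary dropouts, who are already asked to continue, and losses to follow-up, which no wording can recover. Six is therefore an upper bound, at that rate, for outcome-related withdrawals.

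**Assumption.** The unobserved Week 9 MADRS of a withdrawn participant is D points worse than the analysis implies, with D from 5 to 15. The plan gives no figure for D.

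**Formula.** Bias in an arm's mean = (number withdrawn in the arm / 30) × D.

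| Withdrawn | D = 5 | D = 10 | D = 15 |
|---|---|---|---|
| 2 of 60, one per arm (assumed) | 1/30 × 5 = 0.17 | 0.33 | 0.50 |
| 6 of 60, three per arm (upper bound) | 3/30 × 5 = 0.50 | 1.00 | 1.50 |

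These are points per arm, towards too much improvement. With equal losses and the same D the biases cancel in the arm difference. If both of two losses fell in one arm, the difference would be off by 2/30 × D = 0.33 to 1.00. All six in one arm would give 6/30 × D = 1.0 to 3.0, but with equal risk in both arms the chance of that split is only 2 × C(30,6)/C(60,6), about 2.4%.

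**Does the planned model remove the bias?** A random-intercept model with linear time was simulated for one arm of 6,000, with visits at Weeks 0, 3, 5 and 9. All parameters were assumed: baseline 28, true change −9, intercept SD 5, slope SD 0.8 per week, residual SD 4. With the worst 10% withdrawn, the estimated 9-week change, against the full data of the same run, was:

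- withdrawn on worsening already observed at Week 5: −9.57 against −8.97, 0.60 too favourable;
- withdrawn on unobserved Week 9 change: −10.32 against −9.11, 1.21 too favourable;
- withdrawn after Week 3 on underlying trajectory: −10.24 against −8.89, 1.35 too favourable.

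The bias is smaller when the worsening has been recorded but does not vanish. These runs also use the upper-bound 10%, and they show direction and order of size only.

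**The case against.** The strongest reply is that 8.2 is silent on later assessments and does not forbid them, while 12.6.2 states an intention to evaluate everyone. That is fair: a reader might infer that the plan bars further assessment or drops these participants from the analysis, and neither is written. But 12.6.2 gives no procedure for a person already withdrawn, and it sits badly with a section that ends participation and permits replacement.

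A reader might also infer that anyone who gets worse is removed. The documents do not say so: the trigger requires a need for more care than the study provides, a narrower group.

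A third tempting reading is that the randomised comparison is broken, because therapists know which treatment they deliver and 7.11 keeps them unaware only of the hypotheses. Knowledge of the arm is possible, but the documents do not show that withdrawals would differ between arms, and equal losses leave the arm difference unbiased.

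Finally, many section 4.3 exclusions, such as MRI contraindications or a neurological history, have no stated tie to MADRS change. Removal for one of these is a post-randomisation exclusion, and overstated improvement cannot be claimed for it. This limits the point for that trigger but leaves it intact for worsening depression.

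**Conclusion.** The point holds as a gap in outcome collection. Sections 7.10, 8.1, 8.2 and 12.6.2 do not fit together for participants who are withdrawn and did not choose to stop, and they must be reconciled. The loss is clearly outcome-related for worsening depression and for newly developed exclusions that follow from it. Within-arm improvement may then be overstated when the deterioration falls between MADRS visits.

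The likely size is modest: about 0.2 to 0.5 points per arm with one such withdrawal per arm, and at most 0.5 to 1.5 if all of the plan's attrition were of this kind and evenly split. Both ranges rest on the assumed 5- to 15-point gap. The case for acting is that the change is cheap and also protects BADS and the primary rsFC endpoint.

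**What to change.** In 7.10, 8.1 and 8.2, separate stopping therapy from leaving the study. Extend the existing request for the remaining Week 3, 5 and 9 research assessments, and for scans where feasible and not contraindicated, to every randomised participant, including those stopped under 8.2, unless consent is withdrawn. State in section 12 that all randomised participants stay in the analysis in their assigned arm, whether or not they are replaced, and align 12.6.2 with this. A short missing-data sensitivity analysis for MADRS would show how far the result depends on those still lost. The clinical reasons for stopping are unchanged.

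The cost is protocol wording and a few extra ratings, which 6.1 already has done by video. The small downside is that some later data will reflect care received outside the study.

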8.3 Lost to Follow Up

Not Applicable

9. Correlative/Special Studies

Not Applicable

9.1 Laboratory Correlative Studies

Not Applicable

9.1.1 Title – Laboratory Correlative Study #1

9.1.1.1 Collection of Specimen(s)

9.1.1.2 Handling of Specimen(s)

9.1.1.3 Shipping of Specimen(s) (if multicenter)

9.1.1.4 Site(s) Performing Correlative Study (if multicenter)

9.2 Special Studies

Not Applicable

9.2.1 Title – Special Correlative Study #1

9.2.1.1 Assessment

9.2.1.2 Method of Assessment

9.2.1.3 Timing of Assessment

10. Measurement of Effect

Treatment effect will be measured by change in depression severity, resting state functional connectivity in PVS regions, and behavioral activation over the course of treatment.

10.1 Response Criteria

Reduction in depression severity over the course of 9 weeks of treatment (slopes of change in MADRS scores will be calculated within mixed-effects model approach, see Statistical Analysis).

10.2 Duration of Response

Duration of response will be evaluated as reduction in depression severity (measured by the MADRS scale) over the course of 9 weeks of treatment.

10.3 Progression-Free Survival

Not Applicable

10.4 Other Response Parameters

Other endpoints and the criteria for their measurement should be entered below or reference should be made to the protocol section where these criteria may be found.

11. Data Reporting / Regulatory Considerations

11.1 Data Collection

The data collection plan for this study is to utilize REDCap to capture all treatment, efficacy, and adverse event data for all enrolled subjects.

11.1.1 REDCap

REDCap (Research Electronic Data Capture) is a free data management software system that is fully supported by the Weill-Cornell Medical Center CTSC. It is a tool for the creation of customized, secure data management systems that include Web-based data-entry forms, reporting tools, and a full array of security features including user and group based privileges, authentication using institution LDAP system, with a full audit trail of data manipulation and export procedures. REDCap is maintained on CTSC-owned servers that are backed up nightly and support encrypted (SSL-based) connections. Nationally, the software is developed, enhanced and supported through a multi-institutional consortium led by the Vanderbilt University CTSA.

11.2 Regulatory Considerations

11.2.1 Institutional Review Board/Ethics Committee Approval

As required by local regulations, the Investigator will ensure all legal aspects are covered, and approval of the appropriate regulatory bodies obtained, before study initiation.

Before initiation of the study at each study center, the protocol, the ICF, other written material given to the patients, and any other relevant study documentation will be

submitted to the appropriate Ethics Committee. Written approval of the study and all relevant study information must be obtained before the study center can be initiated or the IP is released to the Investigator. Any necessary extensions or renewals of IRB approval must be obtained for changes to the study, such as amendments to the protocol, the ICF, or other study documentation. The written approval of the IRB together with the approved ICF must be filed in the study files.

The Investigator will report promptly to the IRB any new information that may adversely affect the safety of the patients or the conduct of the study. The Investigator will submit written summaries of the study status to the IRB as required. On completion of the study, the IRB will be notified that the study has ended.

All agreed protocol amendments will be clearly recorded on a protocol amendment form and will be signed and dated by the original protocol approving signatories. All protocol amendments will be submitted to the relevant institutional IRB for approval before implementation, as required by local regulations. The only exception will be when the amendment is necessary to eliminate an immediate hazard to the trial participants. In this case, the necessary action will be taken first, with the relevant protocol amendment following shortly thereafter.

Once protocol amendments or consent form modifications are implemented at the lead site, Weill Cornell Medicine, updated documents will be provided to participating sites, as applicable. Weill Cornell Medicine must approve all consent form changes prior to local IRB submission.

Relevant study documentation will be submitted to the regulatory authorities of the participating countries, according to local/national requirements, for review and approval before the beginning of the study. On completion of the study, the regulatory authorities will be notified that the study has ended.

11.2.2 Ethical Conduct of the Study

The Investigators and all parties involved should conduct this study in adherence to the ethical principles based on the Declaration of Helsinki, GCP, ICH guidelines and the applicable national and local laws and regulatory requirements.

This study will be conducted under a protocol reviewed and approved by the applicable ethics committees and investigations will be undertaken by scientifically and medically qualified persons, where the benefits of the study are in proportion to the risks.

11.2.3 Informed Consent

The investigator or qualified designee must obtain documented consent according to ICH-GCP and local regulations, as applicable, from each potential subject or each subject's legally authorized representative prior to participating in the research study. Subjects who agree to participate will sign the approved informed consent form and will be provided a copy of the signed document. Due to COVID-19, informed consent will be obtained over the phone. In our experience, many older adults do not have access to technology that would allow them to consent electronically. An information sheet will be emailed to the participant so that it can be viewed by the participant (or mailed if email is not used). This will allow the participants to review the form thoroughly. Participants will be encouraged

to discuss any concerns or questions they may have with the member of the research team who is conducting the consent. Members of the research team will ensure there is sufficient time to pose questions and will be in contact with the Principal Investigator regarding any potential concerns that need to be addressed. When possible, consent will be conducted over video call within a HIPAA-compliant platform (i.e. Zoom) and the participant could review the consent, presented over video, during the process. Zoom invitations will be sent to participants via email, collected at the initial phone screen phase as contact information and stored in a secured folder that only authorized study team members can access. The same procedures will be used for consent of therapists participating in this study. After the consent form has been reviewed, if informed consent is obtained, the research will sign the "Researcher's statement" portion of the consent form digitally through RedCap in order to have documentation on file.

Participants may opt for an in-person informed consent meeting, which will be conducted in a private interview room located in the Weill Cornell Medicine Psychiatry Department. Participants will have the opportunity to discuss the study in detail with a member of the research study team, ask any questions they may have, and provide their written informed consent by signing the physical consent form. Only the participant and the researcher obtaining consent will be present for the in-person consent procedures.

The initial ICF, any subsequent revised written ICF and any written information provided to the subject must approved by IRB prior to use. The ICF will adhere to IRB requirements, applicable laws and regulations.

11.2.4 Compliance with Trial Registration and Results Posting Requirements

Under the terms of the Food and Drug Administration Modernization Act (FDAMA) and the Food and Drug Administration Amendments Act (FDAAA), the Sponsor-Investigator of the trial is solely responsible for determining whether the trial and its results are subject to the requirements for submission to <http://www.clinicaltrials.gov>. Information posted will allow subjects to identify potentially appropriate trials for their disease conditions and pursue participation by calling a central contact number for further information on appropriate trial locations and trial site contact information.

11.2.5 Record Retention

Essential documents are those documents that individually and collectively permit evaluation of the study and quality of the data produced. After completion of the study, all documents and data relating to the study will be kept in an orderly manner by the Investigator in a secure study file. Essential documents should be retained for 2 years after the final marketing approval in an ICH region or for at least 2 years since the discontinuation of clinical development of the IP. In addition, all subjects' medical records and other source documentation will be kept for the maximum time permitted by the hospital, institution, or medical practice.

12. Statistical Considerations

*All investigator-initiated trials **must** include a study statistician assigned by the Division of Biostatistics and Epidemiology or approval to use alternate biostatistician personnel. Please contact [name] ([contact]) for additional information and assignment*

of a study statistician.

Describe the statistical methods that will be used to analyze the data (chi square, t-test, correlation, etc.)

